A Comparative Study of Retrograde Insertion of a Ureteral Catheter or Not in Total Tubeless Percutaneous Nephrolithotomy

NCT number: Waiting for the number

Version number: V3.0

Release date: October 8, 2022

1. **Title:** A Comparative Study of Retrograde Ureteral Catheter Insertion or Not in Total Tubeless Percutaneous Nephrolithotomy
2. **Registered:** It is intended to be registered in the International Clinical Trial Registry (www.clinicaltrials.gov/).
3. **Trial protocol version and date:** Version3.0/October 8, 2022
4. **Funding Project:** This study was supported by the Clinical Research Project of University of South China (USCKF201902K01), and the Hunan Provincial Clinical Medical Technology Innovation Guiding Project (2020SK51801).
5. **Study participants and responsibilities:** one experienced associate chief urologist performed the surgery, and at least 3-5 researchers participated in data collection and analysis.
6. **The research background and theory:** Total tubeless Percutaneous nephrolithotomy (PCNL) is a modified surgical method of PCNL surgery, that is, there is no indwelling nephrostomy tube and double-J tube during PCNL surgery. Compared with traditional PCNL surgery, it has the advantages of reducing pain, shortening operation time, and reducing operation cost. Since this procedure was first performed in 2004, several randomized clinical studies have verified the safety and efficacy of total tubeless PCNL. With the continuous development of minimally invasive surgery, since the successful implementation of tubeless PCNL in 1997, several randomized controlled clinical studies have verified the safety and feasibility of total tubeless PCNL surgery. With the continuous update of ultrasound equipment and the continuous progress of physician puncture technology, the application of ultrasound guided PCNL surgery is more and more popular. Moreover, ultrasound-guided percutaneous renal aspiration is increasingly independent of retrograde pyelography or artificial hydronephrosis. Therefore, PCNL without reverse insertion of a ureteral catheter has been attempted, especially when patients with severe rheumatoid arthritis or hip ankylosis are clinically encountered, and the lithotomy position is not possible. Passive PCNL without

reverse insertion of ureteral catheter has been successfully performed.

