15. **Recruitment of study subjects:** Recruiting research subjects were conducted by a researcher in the Urology Clinic of the First Affiliated Hospital of the University of South China.

16. **Allocation sequence generation and implementation method:** A researcher was assigned to the group by random number method (odd number represents the conventional tubeless PCNL, and even number represents the total tubeless PCNL without reverse insertion of a ureteral catheter), which took place in the operating room.

17. **Blinding method:** single-blind, the enrolled patients were only told that they could receive either of the two surgical procedures, and the specific surgical method was determined by random number table method after entering the operating room.
18. **Data collection.** All data to be measured: 1. Demographic data, stone characteristics, and preoperative baseline data, including the proportion of gender, age, body mass index (BMI) and basic diseases distribution, location, stones, stone maximum cross-sectional area, the width of hydronephrosis, preoperative hemoglobin, Preoperative hematocrit, preoperative blood leukocyte count, preoperative blood neutrophils ratio, preoperative serum creatinine, urine leucocyte, site of puncture and operation laterality, 2. The primary end point of this study was the rate of postoperative complications, compared according to the modified Clavien-Dindo complication grading system. Observation indexes including postoperative fever, inflammation index change (postoperative blood leukocytes and neutrophils ratio changes value), hemorrhage (value changes of postoperative hemoglobin, red blood cell pressure change value and the incidence of renal subcapsular hematoma), kidney damage (postoperative serum creatinine values change), pain (VAS pain score, non-steroidal anti-inflammatory analgesic, and opioids demand rate) and the incidence of pleural effusion. Secondary end points included stone clearance rate, operation duration, postoperative hospital stay, and hospital costs. 3. Follow-up data included pain, hematuria, fever and readmission for 3 months after operation. Three researchers conducted data statistics respectively and obtained three original data, which were finally averaged.

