19. **Statistical analysis plan:** SPSS26.0 version statistical software was used for analysis. Measurement data were expressed as mean \pm standard deviation ($\bar{X} \pm S$), and Student's t-test was used for intergroup comparisons. The counting data were expressed as frequency and percentage, and the chi-squared or

Fisher's exact probability test was used for intergroup comparisons. The ranksum test was used for grade data. $P < 0.05$ was considered statistically significant.

20. **Approval of informed consent and ethics:** This study followed the ethical standards set out in the Declaration of Helsinki. Informed consent was obtained and signed by all enrolled patients to undergo the two surgical procedures (total tubeless PCNL without reverse insertion of a ureteral catheter and conventional total tubeless PCNL) and to collect and use the medical information and biological samples for the study.
21. **Confidentiality measures:** The identifiable information of the subjects is replaced by irrelevant character sequences to ensure that the relevant personal information of the subjects will not be disclosed in any form.
22. **Declaration of Interest:** There is no conflict of interest between the investigator and the organization.
23. **Data Acquisition:** When proper editing or review requirements are met, the study data may be obtained from the study manager after the study is completed.

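### Section 18's averaging of three researchers' data has no limit by data type and does not fit the yes/no, nominal and graded items it covers (minor)

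*Protocol*

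**What the plan says.** Section 18 of the protocol (Data collection) opens with "All data to be measured" and runs through baseline items, end points and follow-up. The items are of mixed type:

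- continuous: haemoglobin, creatinine, stone area, hydronephrosis width;
- yes/no: subcapsular haematoma, pleural effusion, readmission;
- nominal: sex, and "site of puncture and operation laterality";
- graded: complications, "compared according to the modified Clavien-Dindo complication grading system".

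On the main outcome the section says "The primary end point of this study was the rate of postoperative complications". It closes with the combining rule: "Three researchers conducted data statistics respectively and obtained three original data, which were finally averaged".

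Section 5 describes the staff in terms that cover both extraction and analysis: "at least 3-5 researchers participated in data collection and analysis". Section 17 describes blinding of patients only: "single-blind, the enrolled patients were only told that they could receive either of the two surgical procedures".

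Section 19 assigns tests by data type. Measurement data are given as mean and standard deviation and compared by t-test. For categorical items it says "The counting data were expressed as frequency and percentage, and the chi-squared or" Fisher's exact test is used. Grade data go to the rank-sum test.

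**The concern.** A rule for combining three sets of data matters only where the sets differ. At that point an average makes sense for repeat readings of a continuous quantity, but not for a yes/no item, a side of operation or a complication grade. Section 18 applies the average to the whole list, and section 19 then sends much of that list to tests that need whole categories or whole counts. The two sections therefore do not fit together for discordant categorical data, and the main end point, a complication rate, is within reach of the problem.

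For numeric values that have one true source, such as a laboratory result, an average of three transcriptions is also a weak choice. It dilutes a copying error that a look at the source would remove.

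At stake is whether the analysed values are ones that a patient's record actually supports, and whether the written rule can be followed at all when records differ.

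**Working it through.** The protocol gives no figure to reproduce here. The check takes the rule as written and follows it through each data type.

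**Inputs.** From the protocol: three researchers and an average (section 18); tests by data type (section 19); 100 patients, 50 per group (section 14). Assumed, because the documents give nothing: the error rates, event counts, grade coding and haemoglobin values below.

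**1. Level of averaging.** The wording allows two readings: patient-level records are averaged, or three summary tabulations are. Both are followed.

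**2. Yes/no items, patient level.** The mean of three 0/1 records is 0, 1/3, 2/3 or 1. The two middle values belong to no cell of a 2×2 table, so neither the chi-squared nor the Fisher test can take them.

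With an independent error rate *e* per researcher:

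- P(discordant) = 1 − (1 − e)³ − e³
- P(value held by at least two is wrong) = 3e²(1 − e) + e³

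| Assumed e | Discordant | Patients of 100 | Value wrong after rounding |
|---|---|---|---|
| 1% | 2.97% | about 3 | 0.03% |
| 2% | 5.88% | about 6 | 0.12% |
| 5% | 14.25% | about 14 | 0.73% |

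Fractional values would thus be fairly common, but simple rounding would put nearly all of them right.

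**3. Nominal items.** Left/right and puncture site have no mean.

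**4. Grades, patient level.** With grades coded 0 to 5 (no complication = 0, an assumption), there are 6³ − 6 = 210 discordant ordered triples. Of these, 144 have a sum not divisible by 3 and average to a non-grade. The other 66 average to a whole grade: in 36 it is a grade that someone recorded, in 30 one that nobody recorded (0, 0, 3 gives 1). The rank-sum test still runs on such values.

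For two-against-one splits:

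- grades adjacent: 10 of 10 average to a non-grade, and rounding restores the majority grade in all 10;
- grades two or more apart: rounding restores the majority grade in 0 of 20.

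These counts weight every triple equally. They show what the rule can do, not how often it would.

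**5. Summary level.** Suppose three tabulations give 12, 13 and 13 events in one group. The average is (12 + 13 + 13)/3 = 12.67. Fisher's exact test is not defined for that count. A Pearson chi-squared can still be calculated: 4/50 against 12.67/50 gives p = 0.020.

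Whether rounding 12.67 down or up crosses 0.05 depends on the test:

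| Comparison | Fisher | Chi-squared, continuity-corrected | Chi-squared, uncorrected |
|---|---|---|---|
| 4/50 v 12/50 | 0.054 | 0.056 | 0.029 |
| 4/50 v 13/50 | 0.031 | 0.033 | 0.017 |

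Even with Fisher, such cases are uncommon. With 1 to 20 events in one group and 1 to 19 in the other (380 pairs), adding one event to the second group changes the side of 0.05 in 23 pairs (23/380 = 6%).

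**6. Single-source numbers.** Records of 125, 125 and 115 g/L average to 365/3 = 121.7 g/L. One third of the 10 g/L error (3.3 g/L) stays with that patient. In a 50-patient mean it amounts to 3.33/50 = 0.07 g/L.

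**The case against.** The strongest reply is that the sentence is a loosely worded line, probably translated, and was never meant for categorical data. Section 19 keeps the mean for measurement data, and nobody would in practice average sex or laterality. That may well be what was intended. The text does not say so, however, and writing that limit down is most of the fix.

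A second reply is that handling of discordant records belongs in an SAP or a data-management document, neither of which is shown. This stands against any complaint that the protocol lacks an adjudication or rounding rule, and no such complaint is made here. The point is the rule that the protocol does state, which a later plan for reconciliation would contradict.

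Three stronger readings are tempting, and the documents do not support them:

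- **That every discordant patient gets a value the planned test cannot use.** This follows only if patient-level yes/no records are averaged. If tabulations are averaged, no patient carries a fraction, and only Fisher's test fails. The main end point may also be compared by Clavien-Dindo grade with the rank-sum test, which still runs.
- **That the analyst is forced to pick a rounding rule after seeing the data, with the group known.** Section 17 mentions blinding of patients only, but a rule may be fixed in a document that is not shown.
- **That the averaging could turn the trial's result.** The Fisher example crosses 0.05, but the uncorrected Pearson test on the same counts does not, and the counts are assumed.

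**Conclusion.** The point holds as a minor one. Section 18 states an unlimited averaging rule over a list that includes yes/no, nominal and graded items. When records differ, the rule does not fit the categorical analyses in section 19. How it fails depends on whether records or tabulations are averaged, which the wording leaves open. For single-source numbers it retains one third of a single recording error.

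The size is probably small. Nothing happens where the three records agree. The documents give no discordance rate, so the 3, 6 or 14 discordant patients per 100 rest on assumed, independent error rates. The p-values rest on assumed event counts and on the test chosen, and the grade counts on an assumed coding. No change in the trial's conclusion is shown.

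**What to change.** Replace the closing sentence of section 18 with:

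> Three researchers extract independently; discrepancies are resolved against the source record, by consensus if the source is unclear, as far as practicable without reference to treatment group, and the single verified value is analysed; averaging is used only for independent repeat readings of continuous imaging measurements (stone area, hydronephrosis width).

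The cost is one sentence and a little reconciliation time for researchers whom section 5 already plans; no patients are added. The three sets of data are already to be collected, so the change needs no new extraction. One limit remains: the operative record would be expected to show whether a catheter was placed, so masking during reconciliation may be incomplete without redaction. That is why the wording says as far as practicable.

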catheter implementation process: endotracheal intubation in patients with general anesthesia, prone position after detaching urethral catheter, used in ultrasound guided puncture needle percutaneous renal biopsy to appropriate calyces, under the direct observation of needle in the renal collecting system, using fascia dilator under guide wire step by step coaxial expansion of percutaneous renal channel to 16 Fr or 18 Fr. A rigid nephroscope was inserted and the stone was broken by holmium laser. The crushed stones were removed from the body using constant flow perfusion during stone crushing and stone removal. After checking that there was no residual "visible stone", the puncture sheath was slowly withdrawn, the skin-kidney channel was checked for active bleeding, and the skin incision was closed with suture.

[figure not shown]
The implementation process of conventional total tubeless PCNL:

Endotracheal intubation in patients with general anesthesia, patients were placed in a lithotomy position, and ureteral catheter was inserted reversely under transurethral ureteroscopy and fixed on the urinary catheter. Then, the patients were moved to a prone position and were disinfected again, under the guidance of ultrasound in establishing a channel process and stone removal process was the same as that in total tubeless PCNL without reverse insertion of a ureteral catheter, after inspection without the "visible" stone of residual, The puncture sheath was slowly withdrawn, the passage was checked for active bleeding, and the skin incision was closed with suture.

- 12. Outcome indicators:** The primary end point was the rate of postoperative complications, Observation indexes including postoperative fever, inflammation index change (postoperative blood leukocytes and neutrophils ratio changes value), hemorrhage (postoperative hemoglobin change value, red blood cell pressure change value and the incidence of renal subcapsular hematoma), kidney damage (postoperative serum creatinine change value),

pain (postoperative VAS pain score, non-steroidal anti-inflammatory analgesic and opioids Rate) and the incidence of pleural effusion. Secondary end points included stone free rate, operation time, postoperative hospital stay, and hospital costs.

13. Study flow charts

14. **Sample size:** a total of 100 subjects are expected to be included (50 in each group).

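### Five laboratory change values are compared by an unadjusted t-test although every baseline is collected; adjusting for baseline would usually be more precise at almost no cost (optional, low priority)

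*Protocol*

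**What the plan says.** Section 19 sets one rule for all continuous data. It begins "Measurement data were expressed as mean", adds the standard deviation, and continues "Student's t-test was used for intergroup comparisons". No covariate or baseline adjustment is named.

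Section 12 lists the affected outcomes among the observation indexes under the primary end point: "inflammation index change (postoperative blood leukocytes and neutrophils ratio changes value", "hemorrhage (postoperative hemoglobin change value" and "kidney damage (postoperative serum creatinine change value". Section 18 repeats them, with bleeding given as "hemorrhage (value changes of postoperative hemoglobin, red blood cell pressure change value". I read the last item as haematocrit, because preoperative haematocrit is collected next to haemoglobin. That makes five change values.

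Section 18 also lists the matching baselines: "preoperative hemoglobin, Preoperative hematocrit, preoperative blood leukocyte count, preoperative blood neutrophils ratio, preoperative serum creatinine". Section 14 plans 100 patients, 50 per group, and section 8 calls the study exploratory.

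**The concern.** A t-test on change values is the same as a regression of the postoperative value on group with the baseline coefficient fixed at 1. ANCOVA estimates that coefficient from the data. Both are valid under randomisation. When the true slope is clearly different from 1, fixing it leaves baseline variation in the comparison that could have been removed.

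The five outcomes are the protocol's laboratory measures of inflammation, bleeding and renal injury. With 50 patients per group and no stated power for them, interval width decides how much they can show. What is at stake is efficiency on supporting outcomes only. There is no bias and no inflation of the type I error.

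**Working it through.** **Inputs from the protocol.** 50 per group, N = 100 (section 14); significance at 0.05 (section 19; two-sided assumed). The protocol gives no SD, correlation, effect size or power for these outcomes, so it has no figure of its own to reproduce.

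**Assumed inputs.** Pre/post correlation r = 0.3, 0.5, 0.7, 0.9; ratio of postoperative to preoperative SD k = 1, 1.5, 2; complete data; a linear relation of post to pre.

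**Step 1: variances.** Set the preoperative SD to 1. The true slope is kr.

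- Variance of the change: 1 + k² − 2kr
- Residual variance under ANCOVA: k²(1 − r²)
- The first equals the second plus (1 − kr)², so before the cost of estimating the slope, ANCOVA is never worse and ties only at kr = 1.

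Example, k = 1, r = 0.5: the change variance is 1 + 1 − 1 = 1.00, the residual variance is 1 − 0.25 = 0.75, and the ratio is 0.750.

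**Step 2: cost of estimating the slope.** The expected variance inflation is (N − 3)/(N − 4) = 97/96 = 1.0104, about 1.04%. The error degrees of freedom fall from 98 to 97, which moves the critical value from 1.98447 to 1.98472.

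**Step 3: relative CI width.** Width ratio = √(variance ratio × 97/96) × 1.98472/1.98447. For the example, √(0.750 × 1.0104) × 1.00013 = 0.871.

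**Step 4: power.** The change-score test has 80% power on 98 df at non-centrality 2.829, a difference of 2.829 × √(2/50) = 0.566 SD of the change. ANCOVA's non-centrality is 2.829/√(variance ratio × 97/96) on 97 df.

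| k | r | slope kr | variance ratio | CI width ratio | ANCOVA power (t-test 80%) |
|---|---|---|---|---|---|
| 1 | 0.3 | 0.30 | 0.650 | 0.811 | 93.3% |
| 1 | 0.5 | 0.50 | 0.750 | 0.871 | 89.6% |
| 1 | 0.7 | 0.70 | 0.850 | 0.927 | 85.6% |
| 1 | 0.9 | 0.90 | 0.950 | 0.980 | 81.6% |
| 1.5 | 0.3 | 0.45 | 0.871 | 0.938 | 84.7% |
| 1.5 | 0.5 | 0.75 | 0.964 | 0.987 | 81.0% |
| 1.5 | 0.7 | 1.05 | 0.998 | 1.004 | 79.7% |
| 1.5 | 0.9 | 1.35 | 0.777 | 0.886 | 88.5% |
| 2 | 0.3 | 0.60 | 0.958 | 0.984 | 81.3% |
| 2 | 0.5 | 1.00 | 1.000 | 1.005 | 79.6% |
| 2 | 0.7 | 1.40 | 0.927 | 0.968 | 82.5% |
| 2 | 0.9 | 1.80 | 0.543 | 0.741 | 96.6% |

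**Step 5: when ANCOVA loses.** It is wider only if |1 − kr| < 0.103 × k√(1 − r²). That means a true slope above 0.98 for k = 1, about 0.87 to 1.10 for k = 1.5, and about 0.81 to 1.17 for k = 2. The worst case is a slope of exactly 1: √(97/96) × 1.98472/1.98447 = 1.005, or 0.5% wider.

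**Step 6: simulation.** In 20,000 simulated null trials per (k, r) pair, the mean width ratios agreed with the table to within 0.001. Type I error was 4.7% to 5.2% for both methods. The ANCOVA treatment estimate was the same, to numerical precision, with the change or the postoperative value as outcome.

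**The case against.** The strongest objection is that nothing here is wrong. A t-test on change values under randomisation is a legitimate analysis fixed in advance, and preferring ANCOVA is an efficiency preference. The outcomes are supporting measures in an exploratory trial with no power target, so no claim in the protocol fails if the t-test stays. The gain cannot be shown for any of the five variables: the protocol gives neither SDs nor correlations. Five of the eight cells with k = 1.5 or 2 lie within 2.5 points of 80% power, two of them slightly below it. A separate statistical analysis plan, not shown, could already specify adjustment.

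Most of this stands and sets the rank of the point. It does not remove it. Section 19 is not silent: it assigns an unadjusted test to all continuous data, and that stated choice can be improved. If a separate plan does adjust, the same sentence in section 19 would bring the two into line. The uncertainty is also lopsided, with a loss capped at about 0.5% in expected CI width against a gain that may be material. The tabulated range does not favour the point either: at k = 0.8, over the same correlations, the width ratios are 0.712 to 0.796.

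**Conclusion.** The point holds as an optional, low-priority refinement. The planned test is valid, but baseline-adjusted ANCOVA would usually be more precise for the five laboratory change values.

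Under the assumed inputs its 95% CI is 2% to 19% narrower with equal SDs. With a postoperative SD 1.5 to 2 times the preoperative one, it ranges from 0.5% wider to 26% narrower. The largest gain occurs only at the extreme corner, k = 2 and r = 0.9. Where the true slope is close to 1, ANCOVA gains nothing and is very slightly less precise.

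These sizes rest on assumed correlations and SD ratios, complete data and linearity. The count of five rests on reading one item as haematocrit; without it, four outcomes remain. The complication rate, the named secondary end points and the sample size are unaffected.

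**What to change.** Add one sentence to section 19: each of the five laboratory change values is compared between groups by ANCOVA with treatment group and the same variable's preoperative value as covariate, and the adjusted mean difference is reported with its 95% CI. The outcome remains the change value as defined in sections 12 and 18, and mean ± SD of the change stays as the descriptive summary.

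The cost is one degree of freedom (97 instead of 98), about 1% expected variance per model and the SPSS syntax. No new data are needed.

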Therefore, it is theoretically feasible to carry out total tubeless PCNL without reverse insertion of a ureteral catheter for patients with unobstructed urinary drainage.

7. **Study objective:** The purpose of this study was to evaluate whether without retrograde ureteral catheterization is appropriate for total tubeless PCNL.
8. **Experimental design:** Parallel group design, a total of 2 groups (total tubeless PCNL group without reverse insertion of a ureteral catheter and conventional total tubeless PCNL group) were allocated according to 1:1 or approximately 1:1 for exploratory study.
9. **Study site:** Single-center study, conducted in the Department of Urology, The First Affiliated Hospital of the University of South China.
10. **Inclusion and exclusion criteria:** Inclusion criteria: (1) patients with kidney stones who met the indications for PCNL surgery; (2) the maximum diameter is less than 35mm; (3) the width of hydronephrosis effusion was less than 25mm. exclusion criteria :(1) patients with infectious calculi confirmed by preoperative CT examination and blood biochemical indexes; (2) Patients with severe cardiac and pulmonary insufficiency, coagulation dysfunction and other obvious surgical contraindications; (3) Patients with previous history of PCNL surgery on the affected side or nephrotomy; (4) Patients with indwelling double J tube or nephrostomy tube before operation; (5) Patients with renal trauma or congenital anomalies of urinary system.
11. **Intervention measures:** a. Total tubeless PCNL without reverse insertion of a ureteral catheter and conventional total tubeless PCNL were performed according to the group, and the same deputy chief physician of urology performed the operation according to the random group; B. Symptomatic treatment of patients during perioperative period is allowed, including antiinfection, analgesia, etc.

Total tubeless PCNL without reverse insertion of a ureteral

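### Operation time is compared by an unadjusted t-test although stone cross-sectional area is recorded before surgery; adjusting for it in advance would gain precision at almost no cost

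*Protocol*

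**What the plan says.** Section 19 of the Protocol, which is headed as the statistical analysis plan, gives a single rule for measurement data: "Student's t-test was used for intergroup comparisons". It mentions no covariate, regression model or stratified comparison for any outcome. It does not name operation time, which is covered as a continuous measurement. Section 18 places it among the secondary outcomes: "Secondary end points included stone clearance rate, operation duration, postoperative hospital stay, and hospital costs".

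Section 18 opens its list with "All data to be measured: 1. Demographic data, stone characteristics, and preoperative baseline data", and that list includes "stone maximum cross-sectional area, the width of hydronephrosis". Both are therefore planned for every patient.

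Section 10 limits stone size only from above, "the maximum diameter is less than 35mm", and likewise hydronephrosis, "the width of hydronephrosis effusion was less than 25mm". A further criterion requires that the patient meet the indications for PCNL. Section 16 allocates by odd or even random number and states no stratification. Section 14 plans 50 patients per group.

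**The concern.** Under section 11, the stone in both arms is broken by laser and washed out through a tract of 16 or 18 Fr, and the sheath is withdrawn only at the step that begins "After checking that there was no residual" visible stone. A larger stone should therefore take longer to clear, whichever arm the patient is in. One surgeon performs every operation, so differences between surgeons do not add to the spread, and stone burden is an obvious remaining source of it.

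The unadjusted t-test leaves that variation in the error term. It also takes no account of any difference in stone burden that arises by chance between the two groups actually randomised. The information needed to deal with both is already collected and is used in neither allocation nor analysis. At stake are the width of the confidence interval for operation time and the reading of that result if the baseline table shows unequal stone size.

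**Working it through.** **Inputs from the Protocol.** 50 patients per group (section 14); significance level 0.05 (section 19), taken as two-sided because sidedness is not stated; t-test for continuous outcomes (section 19). Section 14 gives no effect size, SD or power for the 100 patients, so there is no planned power figure to reproduce.

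**Assumptions.** The correlation r between stone area and operation time within arms is not in the documents; it is varied over 0.3, 0.5 and 0.6. The SD of operation time (25 min) and the true difference (12 to 20 min) are illustrative.

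**1. Error variance.** Adjustment multiplies the error variance by 1 − r², and the sample size an unadjusted test would need for the same precision is 100/(1 − r²).

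| r | 1 − r² | Reduction | Equivalent total N |
|---|---|---|---|
| 0.3 | 0.91 | 9% | 100/0.91 = 110 |
| 0.5 | 0.75 | 25% | 100/0.75 = 133 |
| 0.6 | 0.64 | 36% | 100/0.64 = 156 |

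**2. Power.** The standardised difference is d = difference/(25 × √(1 − r²)), with noncentrality d/√(2/50), in a two-sided t-test at 0.05. For 12 min, d = 12/25 = 0.48 unadjusted and 0.48/√0.75 = 0.55 at r = 0.5.

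| True difference | Unadjusted | Adjusted, r = 0.5 | Gain |
|---|---|---|---|
| 12 min | 66.1% | 78.4% | 12.3 points |
| 15 min | 84.4% | 92.9% | 8.5 points |
| 18 min | 94.6% | 98.4% | 3.8 points |
| 20 min | 97.7% | 99.6% | 1.9 points |

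At 12 min, the adjusted power is 70.2% for r = 0.3 and 84.4% for r = 0.6. These figures keep 98 degrees of freedom. Allowing for the estimation of one or two covariates lowers the 12 min adjusted figures by about half a point to one point.

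**3. Chance imbalance.** With 50 per group, the difference in mean stone area between arms has a standard error of √(2/50) = 0.20 SD. The probability that it exceeds 0.3 SD in either direction is P(|Z| > 1.5) = 13.4%. At r = 0.5, an imbalance of 0.3 SD moves the unadjusted difference by 0.3 × 0.5 × 25 = 3.75 min. The unadjusted standard error is 25 × √(2/50) = 5 min. That 5 min already contains the variation due to such imbalances, so the 3.75 min is part of it and must not be added to it.

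**4. Error rate.** In a simulation of 10,000 trials per scenario, with covariates explaining 0 to 50% of the variance and no true difference, the t-test rejected in 4.8% to 5.3% of trials. Across all randomisations it is sound. Among the roughly 13% to 14% of trials with a combined covariate imbalance of at least 0.3 SD, it rejected in about 9%, 15% or 21% when the covariates explained 10%, 30% or 50%. Regression uses the observed imbalance; the t-test does not.

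**5. If the covariates explain nothing.** For a true difference of 0.5 SD, simulated power was 69.8% with the t-test and 69.1% with two useless covariates, a loss of under 1 point.

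**The case against.** The strongest reply is that nothing here is wrong. A t-test on randomised groups is valid, its standard error allows for chance differences in stone burden, and the request is for a more efficient estimator of one of four secondary endpoints in a design that section 8 calls exploratory. All of that stands, and it sets the weight of the point. A separate SAP might add an adjusted analysis, but the Protocol's own section 19 does more than leave the matter open: it chooses the unadjusted test.

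The size of the gain is also uncertain. The correlation, SD and difference are all assumed. If the control arm's extra steps (lithotomy positioning, ureteroscopic catheter insertion, turning and renewed disinfection) count as operation time, which the text does not say, the difference could be large and the gain in power small.

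Four stronger readings are tempting, and the documents support none of them:

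- **That the t-test result is biased by stone burden.** It is not. Only the estimate in a particular unbalanced sample is affected, and the stated standard error covers this on average.
- **That shorter operation time is a main expected advantage of omitting the catheter.** Section 6 credits shorter operation time to total tubeless over traditional PCNL, and both arms here are total tubeless. A time saving can be inferred from the skipped steps, but it is not stated as a main aim.
- **That stone size is unrestricted from below.** The indications for PCNL may exclude small stones, so the spread in stone area cannot be worked out from the 35 mm limit alone.
- **That hydronephrosis width is an equally good predictor.** The documents give neither a mechanism nor a figure for it, so it can only be an optional covariate.

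**Conclusion.** The point holds as a gain in precision and not as the correction of an error. Section 19 sets aside a baseline measurement that, by the described procedure, is likely to be related to operation time. For assumed correlations of 0.3 to 0.6, using it would be worth about 10 to 56 additional patients. The accompanying gain in power ranges from about 12 points to about 2 (SD 25 min, r = 0.5, differences of 12 to 20 min). Adjustment would also correct the estimate for whatever imbalance in stone area the randomisation happens to produce.

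The link between stone area and operation time is inferred from the surgical description, and its strength is unknown. The primary endpoint, the complication rate, is not touched. The change is worth making because it is cheap and because fixing the covariate now avoids choosing an adjustment after an imbalance has been seen.

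**What to change.** In section 19, state that the main analysis of operation time is a linear regression on treatment arm with preoperative stone maximum cross-sectional area as a covariate fixed in advance, entered on the log scale if its distribution is skewed. Hydronephrosis width may be added, provided that this is also decided beforehand. Report the adjusted difference in minutes with its 95% confidence interval, and keep the Student's t-test as a supportive analysis.

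The cost is a sentence or two of text and one or two of the 98 degrees of freedom. No further patients or measurements are needed. If the covariates turn out to explain nothing, the loss is about 1 point of power or less.
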